3.12 Outcome of the Study

3.12.1 Primary Outcome Measures

Change in the number of participants who self-reported that they had quit BQ chewing will be measured through follow-up questionnaire at day 22. This will represent the short-term cessation prevalence achieved by the study.

Change in the number of participants who self-reported that they had quit BQ chewing will be measured through follow-up questionnaire at Month-3. This will represent the intermediate-term cessation prevalence (stay-quit) achieved by the study.

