3.15 Data Management and Analysis

3.15.1 Study variables and operational definition

The baseline questionnaire used in this study contains 6 parts and their variables are as described in the following tables:

Part A – Demographics

Conceptual Definition	Operational Definition	Type of Variable	Scale of Measurement
Age	Participant's age as of last birthday	Continuous/ Numerical	Years
Gender	Participant's gender	Categorical	1- Male 2- Female
Ethnic	Participant's ethnic background	Categorical	1- Bajau 2- Dusun 3- Irranun 4- Malay 5- Chinese 6- Indian 7- Others (specify)
Marital Status	Participant's current marital status	Continuous	1- Single 2- Married 3- Widowed/ Divorcee
Education Level	Participant's highest level of education	Categorical	1- University and above 2- Diploma 3- Certificate 4- STPM/ Matriculation 5- SPM 6- PMR 7- Primary school 8- No formal education
Occupation	Participant's occupation	Continuous	1- House maid 2- Unpaid worker or home maker 3- Self employed 4- Private employee

5- Government or semi government employee

Monthly Income	Participant's monthly individual income	Continuous	1 < RM 500 2 RM 501 – RM 999 3 RM 1000 – RM 2999 4 RM 3000 - RM 4999 5 RM 5000 and above
----------------	---	------------	--

Part B – BQ Chewing Behaviour & Other Concomittant Risk Habits (Maling TH, 2016 & Tahir Z et al., 2003)

Conceptual Definition	Operational Definition	Type of Variable	Scale of Measurement
Current Chewing Status	Did the participant chewed at least 1 BQ for the past 1 week	Categorical	0- No such habit 1- Habit currently practised 2- Past habit and now has stopped
Age started chewing	What was the age the participant started chewing BQ	Continuous/ Numerical	
Years have ceased the habit (for ex-chewers)	How long the ex-chewer has ceased the BQ habit	Categorical	1- A month ago 2- 3 months ago 3- About a year ago 4- Already more than 5 years
Frequency of chewing BQ	How often current BQ chewers chewed BQ	Categorical	1- Daily 2- Two-three times a week 3- Few times a month 4- I am an occasional betel quid chewer 5- Others, please specify
Number of BQ chewed per day	Number of BQ chewed by the participants in a day	Continuous/ Numerical	
Special practice (relevant to Kota Belud)	Do participants keep their BQ in their mouths overnight	Categorical	1- Yes 2- No

Past quit attempts	If the participants have attempted quitting chewing before in their life	Categorical	1- Yes 2- No

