Appendix M - Follow-Up Questionnaires

ID			
	
JABATAN KESIHATAN PERGIGIAN MASYARAKAT DAN PENCEGAHAN KLINIKAL
 
Cross-Cultural Adaptation of a Betel Quid Cessation Program and Evaluation of Its Effectiveness in A Malaysian High-Risk Community
 
[name] [name], [name]. [name], Associate [name]. [name]
		
FOLLOW-UP QUESTIONNAIRE			Office use

Date of Program: _____
 
Name (as in Identity Card): _____
 
Address (current home address): _____ _____
 
Telephone No.: _____
 
No. Intervention Session Attended.: _____
 
Reasons for Absence (if any): _____
			

1. What is your current betel quid chewing status?
 
d. No such habit (proceed to xx)
 
e. Habit currently practiced
 
f. Past-habit and now has stopped
	  		 B1

2. For current chewer, how often do you chew betel quid now?
 
a. Daily
 
b. 2-3 times a week
 
c. Few times a month
 
d. I am an occasional betel quid chewer
 
e. Others, please specify: _____
	   		 B2

3. How many quid(s) do you chew in a day?
	 		 B3

4. What is (are) the ingredients that you use in your betel quid?
 
a. Areca nut
 
b. Tobacco
 
c. Betel leaf
 
d. Lime
 
e. Gambir
 
f. Others
 
(If yes, please specify: _____)
	    		 B4

The End

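### Month 3 is labelled stay-quit, but the follow-up form records only current chewing status, with no look-back window and no date of last chew

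*Protocol*

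**What the plan says.** - **Outcome.** Under Section 3.12.1 the number of participants who say they have quit "will be measured through follow-up questionnaire at Month-3". The section then states: "This will represent the intermediate-term cessation prevalence (stay-quit) achieved by the study".
- **Instrument.** Item 1 of Appendix M asks: "What is your current betel quid chewing status". The answer for a quitter is "Past-habit and now has stopped". The other items cover frequency, quids per day and ingredients.
- **Frequency item.** It is addressed to current chewers. Its options include a few times a month and "I am an occasional betel quid chewer".
- **Only stated window.** Section 3.15.1, Part B, defines current chewing status as: "Did the participant chewed at least 1 BQ for the past 1 week". The tables are introduced with: "The baseline questionnaire used in this study contains 6 parts and their variables are as described in the following tables". There is no matching table for the follow-up questionnaire.
- **Timing.** In the intervention arm Quit Day is Day 15. The Day 22 session expects some participants to have relapsed (Section 3.10.3.2). Status is asked at Day 22, 1 month and 3 months (Sections 3.10.1.1 and 3.14).
- **Saliva.** Section 2.11 reports that areca alkaloids return to baseline after 8 hours and can be followed only short term.

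**The concern.** Stay-quit says that a person stopped and remained stopped. A single question on present status cannot show that, and this one does not say what period the present covers. If the form is used as printed, a primary result reported under this label would include people who were chewing for much of the follow-up. Readers would take a snapshot for maintained abstinence. The gap cannot be closed at analysis, because no analysis plan can recover a date of last chew that was never asked.

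**Working it through.** **1. What the label needs, and what the form collects**

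| Needed to call someone stay-quit at Month 3 | Provided? |
|---|---|
| A stated period without chewing | No |
| Date of last chew, or time since stopping | No. Baseline item B3 asks ex-chewers how long ago they stopped; Appendix M drops it |
| Any chewing since Day 15 or Day 22 | No |
| A rule linking Month 3 status to earlier visits | Not in Section 3.12.1 |

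Section 3.10.1.1 also says that follow-up will record quit attempts since the start of the intervention. Appendix M has no such item.

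**2. Three histories put through the form at Month 3**

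- Quit on Day 15 and never chewed again: ticks the stopped option.
- Quit on Day 15, relapsed after Day 22, chewed for weeks, stopped shortly before the visit: ticks the stopped option.
- Still chewing at Day 22, first quit later: ticks the stopped option.

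All three count as stay-quit under Section 3.12.1. Only the first fits the term.

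**3. Can other data separate them?**

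- Saliva: no. The look-back is about 8 hours, while Day 22 to Day 90 is 90 − 22 = 68 days.
- Status at Day 22 and 1 month: partly. It would expose the third history if the outcome were defined across visits, which it is not. It would not show chewing between visits, and it uses the same item without a window.

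**4. Why the window must be stated**

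The form treats a person who chews a few times a month as a current chewer. A past-week rule would often not. As an illustration only, assume that chewing episodes follow a Poisson process at r per 30-day month, so that P(none in 7 days) = exp(−7r/30).

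| r per month | Chance of no chewing in the past week |
|---|---|
| 1 | 79% |
| 2 | 63% |
| 3 | 50% |
| 4 | 39% |

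The same person may be a quitter or a chewer depending on the rule. So a past-week question alone would not settle the matter, and the date of last chew is needed as well.

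**5. Range of the possible size**

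The documents give no relapse rate. Section 3.4 plans on 38.64% and 9.09% quitting. Its total of 76 reproduces with the two-sided, continuity-corrected formula for two proportions (alpha 0.05, power 0.8), which gives 38 per arm. Assume that these are Month 3 snapshot rates (the protocol does not say) and that the same share q of snapshot quitters in each arm was not continuously abstinent. The sustained rate is then p × (1 − q). N below is the total before dropout by the protocol's own method.

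| q | Intervention | Control | N |
|---|---|---|---|
| 0 | 38.6% | 9.1% | 76 |
| 10% | 34.8% | 8.2% | 88 |
| 20% | 30.9% | 7.3% | 102 |
| 30% | 27.1% | 6.4% | 120 |
| 50% | 19.3% | 4.5% | 176 |

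This table does not decide whether the label is supported. It shows only how far a sustained rate could fall below the snapshot rate, and why stay-quit should not become the primary outcome at the present sample size.

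**The case against.** The best defence is that the label is one loose parenthesis. The same sentence says prevalence, and the hypothesis in Section 1.7 speaks of a cessation rate at the 3-month assessment without calling it sustained. Status is collected at three visits. The form is visibly unfinished ("No such habit (proceed to xx") and is still due for validation, pre-test and pilot (Sections 3.10.1.4 and 3.10.2). A derivation rule may sit in an analysis plan that is not shown.

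Much of this stands. The protocol nowhere promises continuous abstinence, and its other wording fits point prevalence. That makes stay-quit the term out of place. It does not supply a window or a date of last chew, and a derivation rule cannot work on items that were not asked.

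Some stronger readings are tempting but not supported:

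- **That the form contradicts the one-week definition.** That definition is written for the baseline questionnaire. Used as printed, the follow-up form steers infrequent chewers to the current-chewer answer. The fault is that no window is stated for follow-up.
- **That the look-back covers only 7 of 75 days, about 9%.** This imports the baseline week into a form that has no window. Even then it would measure coverage, not error.
- **That the error favours the intervention arm because its programme teaches cutting down.** The fading method applies before Quit Day, the booklet given to both arms also promotes reduction, and no figure shows more infrequent chewers in one arm at Month 3.
- **That the no-such-habit answer distorts the count.** A person who ticks it is a non-chewer either way.

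**Conclusion.** The point holds as a mismatch between the label of a primary outcome and its instrument. As printed, the Month 3 item gives current self-reported status over an unstated period. It cannot distinguish maintained quitting from a late quit or from a relapse that ended shortly before the visit, and saliva cannot make up for this. The conclusion rests on the text of Section 3.12.1, Appendix M, Section 3.15.1 and Section 2.11, and needs no numerical assumption. The size is unknown. The ranges in the working depend on assumed chewing patterns and relapse shares, and no direction of bias between arms is established. The change should be made before field work, because the missing item cannot be added afterwards.

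**What to change.** 1. **Appendix M, at Day 22, 1 month and 3 months:** add *When did you last chew betel quid?*, answered as a date or as days ago. Baseline item B3 should not simply be copied, since its shortest category is a month ago.
2. **Appendix M, status item:** print one look-back window, for example the protocol's own past week. From Day 15 to Day 22 is 22 − 15 = 7 days, so the form should say whether the first day of the window counts.
3. **Section 3.12.1:** call the Month 3 outcome point-prevalence cessation over that window.
4. **Stay-quit:** report it only for participants who are quit at Day 22, 1 month and Month 3 and whose last chew was before Day 22. Day 22 is a visit in both arms, whereas the protocol describes a Quit Day only for the intervention sessions.

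The cost is one new question, one added phrase on an existing item and a short edit to Section 3.12.1. All can be tested in the planned pre-test and pilot. The downside is that the stay-quit rate will be lower than the snapshot rate and will rely on recall.

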3.12.2 Secondary Outcome Measures

Levels of areca nut biomarkers in saliva samples will be tested via liquid chromatography mass spectrometry at day 22. The cut-off levels for areca nut biomarkers are arecoline (60 ng/mL), arecaidine (10 ng/mL), guvacoline (20 ng/mL), and guvacine (6 ng/mL) and cotinine (10 ng/mL). Biomarkers level above this cut-off points represent that participants are still practicing the habit and have not ceased the habit.

Levels of areca nut biomarkers in saliva samples will be tested via liquid chromatography mass spectrometry at Month-3. The cut-off levels for areca nut biomarkers are arecoline (60 ng/mL), arecaidine (10 ng/mL), guvacoline (20 ng/mL), and guvacine (6 ng/mL) and cotinine (10 ng/mL). Biomarkers level above this cut-off points represent that participants are still practicing the habit and have not ceased the habit.

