2.11 Saliva Biomarkers of Areca Nut

Nair J et al. (1985) was one of the first researchers that studied the exposure of tobacco-specific and areca nut-specific N-nitroso compounds in saliva among BQ chewers who incorporated tobacco and without tobacco. The study found arecoline (AN specific alkaloid) at high levels in the saliva of both type of BQ chewers; with or without tobacco. Nicotine and cotinine were also present in the saliva of BQ chewers who added tobacco.

Huang JL et al. (1989) developed a simple and rapid method to simultaneously determine the 4 major alkaloids in AN which was the high-performance liquid chromatographic (HPLC) determination. Through this method, the author concluded that all four major levels of AN alkaloids can be determined and was higher than the previous study. The study used fresh AN as sample.

Franke AA et al. (2015) performed a chemical analysis study to identify saliva compounds which were specific to the 3 most common preparations of AN used in the study site (Guam); red, matured areca nut only (BN group), red, matured areca nut wrapped in betel leaf (BL group) and green, young areca nut wrapped in betel leaf, slaked with lime and incorporated with tobacco (BQ group). The study showed the **predominant compounds in saliva from those chewing AN were guvacine, arecoline, guvacoline, and arecaidine** and the predominant compound in the betel leaf and saliva from those chewing the leaf was chavibetol.

Guvacine levels were 6 times higher in the matured AN extracts compared to young AN extracts (1, 871.4 ug/g vs. 302.9 ug/g) whereas **arecaidine levels were 2 times higher in the young AN extracts** compared to the matured AN extracts (93.2 vs. 47.7 ug/g). **Chavibetol was the main constituent** of and were exclusively found in the **betel leaf**

extracts at a concentration of 39,873.8 ug/g. **Nicotine was the major alkaloid in the tobacco extracts** (15,454.8 ug/g) with a slight amount of it detected in the AN and leaf extracts (0.1 – 1.4 ug/g) (Franke AA et al., 2015).

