Franke AA et al., in 2016 conducted a pilot study to further explore the pharmacokinetics of AN's alkaloid as those assessment of biomarkers was very in need to evaluate the effectiveness of BQ cessation program that was targeted to reduce the oral cancer burden in the high-risk areas in Hawaii. The study found that AN alkaloids; **arecoline, guvacoline, guvacine, and arecaidine were detected in saliva of all participants and peaked within the first 2 hours post-chewing before returning to baseline levels after 8 hours**. The salivary chavibetol was reported in participants consuming betel leaves in their quid and it peaked 1-hour post-chewing. Thus, the study concluded the AN biomarkers from saliva can be followed up only on a short-term basis (≤ 8 h post-chewing). The study too claimed to find similar AN alkaloids from urine samples of the participants.

Franke AA et al. (2022) reported that **saliva bio verification results are valid to be used to verify the self-reported chewing status of participants ('quitter' or 'chewer') at day 22 follow-up to evaluate cessation program's effectiveness**. In the BENIT trial, among the quitters, the decrease in AN compounds were most significant for arecoline ($p=0.044$), followed by arecaidine ($p=0.042$) and nicotine ($p=0.011$). Among the current chewers, the significant decrease was noted only for hydroxycotinine ($p=0.004$).

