3.10 Conduct of the Study

There will be 3 phases to the conduct of this study as below:

- Phase 1 Adaptation, Validation and Translation of the Questionnaire,
Educational Booklet and Intervention Module**
- Phase 2 Pretest and Pilot test of the study**
- Phase 3 Implementation of the study (Field Work)**

The conduct of the study will be discussed in detailed manner according to the phases of the study.

3.10.1 Phase 1 Adaptation, Validation and Translation of the Questionnaire, Educational Booklet and Intervention Module

In Phase 1, there are 3 components that will undergo the adaptation; namely the baseline and follow-up questionnaire, educational booklet and intervention module. The details of these 3 components are described below in 6.10.1.1 till 6.10.1.3.

BENIT trial (Paulino YC et al., 2020) was selected as the intervention of choice to be cross-culturally adapted in Malaysia due to few reasons. Firstly, this is the first intervention of its kind that targets primarily the users of betel quid in an indigenous population that utilises areca nut. Other researches focusses more on smokeless tobacco. As Malaysian high risk community are more common to use areca nut singly and mostly without smokeless tobacco, thus BENIT was selected to be adapted in Malaysia for this study. There are other studies too from Pakistan that focusses on adolescents. Since the population that chews betel quid in Malaysia are above 40 years old, thus BENIT again was a more appropriate intervention to be adapted in Malaysian high risk community.

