3.11.5 LCMS analysis

The lab test will be run by staff at the Biotechnology Research Institute (BRI), Universiti Malaysia Sabah (UMS). The BRI lab is located at Kota Kinabalu, Sabah which is about 1 to 1.5 hours from the study site and precaution will be taken to deliver samples within 8 hours after collection due to the quick disappearance property of areca nut biomarkers after 8 hours of collection.

LCMS analysis will be carried out on a model Accela ultra HPLC system coupled to a Q Exactive Orbitrap Mass Spectrometer and a CTC PAL autosampler (all from Thermo-

Fisher, San Jose, CA). 10 µl of the above mixture will be injected into a Kinetex C18 column (150 x 3 mm, 2.6 µm, Phenomenex, Torrance CA) with a Phenomenex UHPLC C18 pre-column (3.0 mm i.d.).

Gradient elution will be performed at a flow rate of 300 µL /min using 10 mM ammonium hydroxide in H₂O (A) and 10 mM ammonium hydroxide in MeOH (B) as follows: 0-15.0 min linear gradient from 65%A to 20%A; 15.0-20.0 min hold at 20%A; 20.0-20.1 min increase to 65%A then to equilibrate it for 5 minutes. Total HPLC time including equilibration will be around 25 minutes.

Mass analysis will be performed under positive and negative electrospray full scan mode, the conditions will be as follows: (+) ESI spray voltage 4.5 kv, capillary transfer temperature 350 °C, (-) ESI spray voltage 3.5 kv, capillary temperature 320 °C; and other parameters will be: HESI heater temperature 200 °C, sheath gas flow rate 30 unit; auxiliary gas 5 unit, in-source CID 5 ev, scan range 100 ~ 1000. AGC target 1e6, maximum injection time 100 ms, resolution 35,000, microscan 1.

Quantitation of all analytes will be performed with Xcalibur™ software by extracting the within 5 ppm of the calculated exact masses as according: Arecoline and Arecoline-d5 at +ESI [M+H]⁺ 156.10191 and 161.13329; Guvacoline at +ESI [M+H]⁺ 142.08626, Guvacine at +ESI [M+H]⁺ 128.07061, Arecaidine at +ESI [M+H]⁺ 142.086, NNN at +ESI [M+H]⁺ 178.09749, NAT at +ESI [M+H]⁺ 190.09749, NNK and NNK-d3 at +ESI [M+H]⁺ 208.10805 and 211.12688, Nicotine and Nicotine-d4 at +ESI [M+H]⁺ 163.12297 and 167.14808, Cotinine and Cotinine-d3 at +ESI [M+H]⁺ 177.10224 and 180.12107, N-nitrosoguvacoline at +ESI [M+H]⁺ 171.07642, Hydroxycotinine at +ESI [M+H]⁺ 193.09715, and chavibetol at -ESI [M-H]⁻ 163.07590 (Franke AA et al,2015).

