3.14.2 Follow up at 22-day (short term)

Information regarding participant's personal particular, participant's compliance, current chewing status, number of cut-down of habit by the participants (quid/day), total number of session attended and reasons if absent and the BQ composition if participants are still chewing will be gained through a face-to-face interview with a follow-up questionnaire.

Participant's 22-day saliva samples will be gained to evaluate the short term effectiveness of the intervention and to verify the self-reported outcomes. The levels of areca nut and cotinine biomarkers in saliva samples (via liquid chromatography mass spectrometry) will be evaluated. The cut-off levels for areca nut biomarkers are arecoline (60 ng/mL), arecaidine (10 ng/mL), guvacoline (20 ng/mL), and guvacine (6 ng/mL) and the cut-off levels for cotinine levels (10 ng/mL). Biomarkers level above this cut-off points represent that participants have still not ceased the habit.

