3.14.3 Follow up at 1-month and 3-month

Information regarding participant's personal particulars, participant's current chewing status, number of cut-down of habit by the participants (quid/day) and the BQ composition if participants are still chewing will be taken through face-to-face interview with a follow-up questionnaire.

At 3-month, participants' saliva samples will be collected to evaluate the intermediate term effectiveness of the intervention and to verify the self-reported outcomes. The same cut-off levels of AN and cotinine will be used to represent the participant's cessation of their chewing habit.

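### The saliva rule counts cotinine, a tobacco marker, as continued betel-quid chewing, and lets a sample that looks back about 8 hours stand for cessation

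*Protocol*

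**What the plan says.** Saliva is a secondary outcome at Day 22 and Month 3 (section 3.12.2). The cut-offs are arecoline 60, arecaidine 10, guvacoline 20, guvacine 6 and cotinine 10 ng/mL, and their meaning is fixed: "Biomarkers level above this cut-off points represent that participants are still practicing the habit and have not ceased the habit". Section 3.14.2 repeats this for Day 22: "Biomarkers level above this cut-off points represent that participants have still not ceased the habit". For Month 3, section 3.14.3 says "saliva samples will be collected to evaluate the intermediate term effectiveness of the intervention and to verify the self-reported outcomes". It then turns the rule round: "The same cut-off levels of AN and cotinine will be used to represent" that the participant has ceased chewing.

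The background and design sections say the following about the same markers:
- Section 2.11, on an early saliva study: "Nicotine and cotinine were also present in the saliva of BQ chewers who added tobacco".
- Section 3.10.1, on the target community: areca nut users there are "more common to use areca nut singly and mostly without smokeless tobacco".
- Section 3.8 makes tobacco in the quid optional and does not exclude smokers.
- Section 2.11, on the pharmacokinetic pilot study: the areca "biomarkers from saliva can be followed up only on a short-term basis", given as 8 hours or less after chewing.
- Appendix C asks about smoking at baseline. The four items in Appendix M ask about neither smoking nor time since the last chew.

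**The concern.** Salivary biomarkers are one of the two effectiveness measures in objective iv (section 1.6.2) and the stated check on self-report. A check of this kind should fail people who chew and pass people who do not. Cotinine responds to tobacco from any source, so it can fail someone who has stopped betel quid but still smokes. The areca alkaloids are specific to the habit but short-lived, so they can pass someone who still chews but not in the hours before the visit. As written, the report could record genuine quitters as chewers and present the absence of recent chewing as cessation.

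**Working it through.** **1. The two plain readings of the cut-off rule.** The protocol does not say whether one marker or all five must exceed the cut-off.
- Any marker: a smoker who has quit betel quid and has cotinine above 10 ng/mL is classed as still chewing.
- All markers: section 2.11 gives nicotine as 15,454.8 ug/g in tobacco against 0.1 to 1.4 ug/g in nut and leaf. A chewer with no tobacco exposure would in practice stay below the cotinine cut-off and so never be positive.

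**2. How many chewers smoke (section 2.1, intercountry study, Malaysia).**
- Men: 4.1 + 3.8 + 0.2 + 1.7 = 9.8%, which reproduces the current-chewer prevalence in Table 2.1. Smokers: (4.1 + 3.8)/9.8 = 7.9/9.8 = 81%.
- Women: 27.8 + 1.2 + 0.4 + 0.1 = 29.5%, again as in Table 2.1. Smokers: (1.2 + 0.1)/29.5 = 1.3/29.5 = 4%.
- Equal numbers of men and women in the population would make men 9.8/(9.8 + 29.5) = 25% of chewers. The overall smoker share is then s = (7.9 + 1.3)/39.3 = 23.4%. With women only, s = 4.4%.

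**3. Share of true quitters misclassified, any-marker reading.** Assume that every smoker exceeds 10 ng/mL cotinine and that non-smoking quitters do not. Let r be the smokers' quit rate relative to non-smokers. The share is s·r/(1 − s + s·r).

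| Sample | r = 1 | r = 0.5 | r = 0 |
|---|---|---|---|
| All female, s = 0.044 | 4.4% | 2.3% | 0% |
| 25% male, s = 0.234 | 23.4% | 13.3% | 0% |

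The value r = 0.5 is an assumption. Section 2.4.2 supports only its direction, reporting that ex-smokers were about twice as likely to quit as current smokers.

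**4. Effect on the comparison.** With equal smoking in both arms and r = 1, each arm's rate is multiplied by 1 − s. Taking the section 3.4 planning rates as unverified self-report (an assumption), the ratio 38.64/9.09 = 4.25 is unchanged. The difference of 29.6 points becomes 29.55 × 0.956 = 28.2 (all female) or 29.55 × 0.766 = 22.6 (25% male).

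**5. What a negative sample can show.** The entry minimum of 2 to 3 episodes a week (section 3.8) means an average gap of 168/3 = 56 to 168/2 = 84 hours between chews, against a window of at most 8 hours. At three evenly spaced quids a day the gap is 24/3 = 8 hours, so frequent chewers would mostly be caught. The gap in the check therefore concerns infrequent chewers who report having quit.

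**The case against.** **Combining the markers may be left to the SAP.** That is fair, and section 3.14.2 names cotinine's cut-off apart from the areca ones. Tobacco in the quid is recorded, so cotinine could be read only for tobacco-quid users. Section 2.11 also reports a fall in nicotine among quitters in the earlier trial (p=0.011). But the protocol states no such restriction. A former tobacco-quid user who smokes would still be failed, and the same paragraph reports a fall in hydroxycotinine among continuing chewers (p=0.004). The marker list and its meaning are already fixed in the protocol.

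**The stated purpose is to verify self-report, which is close to a combined definition.** This stands, and it makes the second part of the point mainly one of wording. It does not remove the sentence in section 3.14.3 that lets the cut-offs represent cessation.

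**Stronger readings that the documents do not support:**
- A reader might compute that 1 − 3 × 8/168 = 86% to 1 − 2 × 8/168 = 90% of continuing chewers are missed at a minimum. Section 2.11 says levels return to baseline but does not relate baseline to the cut-offs, so this is not a minimum. It also takes the lowest entry frequency and a random sampling time, and it counts chewers who admit chewing, whom self-report already classifies.
- A reader might see this as a Month 3 problem only. The 8-hour limit applies equally at Day 22. Month 3 differs in that the validation cited in section 2.11 is for Day 22.
- A reader might take section 3.11.5, with its "quick disappearance property of areca nut biomarkers after 8 hours of collection", as a misquotation of the post-chewing window. That sentence is a sample-transport precaution, and rewording it would leave the delivery limit without a reason.
- A reader might infer damage to the primary result or the sample size. The primary outcome is self-reported (section 3.12.1), and the protocol defines no saliva-verified endpoint for which power was planned.

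**Conclusion.** The cotinine rule is wrong as written and should be corrected. The protocol's own text shows that it measures tobacco exposure, in a trial that admits smokers and expects mostly tobacco-free quids. The size is uncertain: about 4% to 23% of true quitters under the any-marker reading with equal quitting, lower if smokers quit less often, and none if no smoker quits. These figures rest on national smoking shares that are not specific to the Bajau, and on all smokers exceeding the cut-off. With equal smoking in both arms the rate ratio does not change.

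The second part holds in a limited form. A value below the cut-offs at Day 22 or Month 3 shows no recent chewing, not sustained cessation. It could miss infrequent chewers who report having quit, but the share missed cannot be fixed from the documents.

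**What to change.** - In sections 3.12.2, 3.14.2 and 3.14.3, take cotinine out of the chewing rule and report it separately as tobacco exposure.
- Define saliva-verified cessation at both visits as self-reported quit AND no areca alkaloid above its cut-off. Describe it as no recent chewing (about 8 hours), and do not let a value below cut-off represent cessation on its own.
- Add two items to Appendix M: hours since the last chew, and current smoking.
- Leave section 3.11.5 unchanged.

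The cost is protocol wording and two short questions, with no extra samples or assays. The price is a weaker claim from a negative saliva test.
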